4.5 Handling of Censored and Missing Menstrual Blood Loss (MBL) Data

Subjects in the HMB subgroup will collect their used sanitary products during 4 periods of 30 days as described in Integrated Protocol Section 9.1 and Integrated Protocol Table 9–2, i.e. for the following study days:

- beginning of Year 6, i.e. 30 days after baseline visit = study days 2-31
- end of Year 6, i.e. 30 days prior to Visit 4 (-14 days) = study days 322-351
- end of Year 7, i.e. 30 days prior to Visit 6 (-14 days) = study days 687-716
- end of Year 8, i.e. 30 days prior to Visit 8 (-14 days) = study days 1052-1081

MBL data will be available per HMB subject per collection period per day per sanitary product.

The cumulative volume of MBL will be calculated per HMB subject per analysis period (as described in Section 6.2.2) which is the basis for the secondary efficacy variables.

Since MBL is related to the bleeding intensity (which is recorded by the subject on a daily basis in the eDiary):

- missing bleeding intensity data will be imputed using the same approach described in Section 4.4, but imputations will be based on the 30-day collection period for MBL data (i.e. bleeding diary data prior to the ‘extension treatment period’ will be included, for subjects who had their baseline visit prior to the start of the ‘extension treatment period’)
- missing MBL data will be imputed depending on the subject’s daily (imputed) bleeding intensity, as described in the following paragraphs.

[figure not shown]
Different types of (complete/ incomplete/ missing) MBL data are expected in a 30-day collection period, ^{CCI} 

Statistical Analysis Plan (Supplement)

CCI

CCI

4.6 Interim Analyses and Data Monitoring

No formal interim analysis in the sense of a group sequential or adaptive design is planned. However, an analysis of the data is planned after Year 6, i.e. after all subjects have prematurely discontinued or completed Visit 4, i.e. treated with Mirena for up to 6 years (1 year in the study). Another analysis of the data is planned after Year 7, i.e. after all subjects have prematurely discontinued or completed Visit 6, i.e. treated with Mirena for up to 7 years (2 years in the study). These will cover the full set of analyses as described in the SAP on hand, unless otherwise stated.

For the analysis after Year 6, cumulative data will be used up to the end of Year 6; each subject's data will be cut-off after she has completed Visit 4 or prematurely discontinued (whichever occurs first). For the analysis after Year 7, cumulative data will be used up to the end of Year 7; each subject's data will be cut-off after she has completed Visit 6 or prematurely discontinued (whichever occurs first). Subjects who have completed Visit 4 and Visit 6, respectively, still wearing the Mirena will be considered ongoing subjects.

4.7 Data Rules

Start date of 'treatment period'

The date of baseline visit will be considered the start date of the 'treatment period', i.e. study day 1.

Start date of study drug administration, i.e. start date of 'extension treatment period'

Day 1 of Year 6 of Mirena use will be considered the start date of study drug administration.

Date Mirena last known in situ

The 'date Mirena last known in situ' is referred to in Integrated Protocol Section 10.3.2.1 and Integrated Protocol Table 10-1 and is needed to calculate the crude exposure time for PI calculation for subjects who were lost to follow-up (e.g. because the woman withdrew consent, was lost to follow-up, or died) and for ongoing subjects (during the analyses after Year 6 and Year 7).

The 'date Mirena last known in situ' will be the latest date when the subject was found to be compliant with Mirena, before the first occurrence of non-compliance (if any).

Compliance/non-compliance is described in Section 6.1.3.5 and Integrated Protocol Section 9.6.3.8.

Therefore, the 'date Mirena last known in situ' will be the latest of the following:

- Last date (before the first occurrence of non-compliance, if any) when Mirena threads were visible
- Last date (before the first occurrence of non-compliance, if any) when Mirena location was found to be "In situ" or "Displaced, intrauterine"

If any of these dates is missing or partial, it will be imputed individually as described in Section 4.3.

Stop date of study drug administration

If the Mirena was totally expelled or removed during the study, the stop date of study drug administration will be the date of Mirena expulsion or removal.

If the Mirena was not totally expelled or removed during the study (e.g. because the woman withdrew consent, was lost to follow-up, or died), the stop date of study drug administration will be the 'date Mirena last known in situ'.

For ongoing subjects (during the analyses after Year 6 and Year 7), the stop date of study drug administration will be the 'date Mirena last known in situ'.

Woman-years

One woman-year will comprise 365 days of study treatment exposure, unless otherwise stated.

Treatment-emergent AEs

The onset date of AEs will be used to distinguish between treatment-emergent and pre-treatment AEs. If an event occurred on Day 1 of Year 6 of Mirena use or later, it will be considered as treatment-emergent AE. Otherwise, it will be considered as pre-treatment AE.

AEs in 6th / 7th / 8th year

The onset date of treatment-emergent AEs will be used to distinguish between AEs in 6th, 7th and 8th year:

- If [Day 1 Year 6 \leq onset date \leq Day 1 Year 6 + 364 days], it will be considered an AE in 6th year
- If [Day 1 Year 6 + 365 days \leq onset date \leq Day 1 Year 6 + 729 days], it will be considered an AE in 7th year
- If [Day 1 Year 6 + 730 days \leq onset date], it will be considered an AE in 8th year (including any AE which may fall into the beginning of Year 9)

Mapping of selected assessments to regular study visits

For subjects who discontinued study treatment prematurely at the timing of one of their regular study treatment visits (i.e. Visits 3, 4, 5, 6 or 7), data will be recorded on the electronic case report form (eCRF) in the End of Treatment (EOT) folder (i.e. EOT / Visit 8).

For the statistical analysis selected assessments will be mapped to regular study treatment visits as described in the following paragraphs, in order to ensure meaningful presentation of information on a visit level, e.g. in summary tables by visit.

The following assessments will be mapped:

- Vital signs
- Checking of Mirena threads
- Pregnancy test
- Urine Sample Collection for Central Lab
- Blood Sample Collection for Central Lab
- Assessment of laboratory results
- Pharmacokinetic (PK) Sample Collection (single sample – blood)
- Continuing Need for Contraception
- Subject satisfaction with Mirena

If study treatment was discontinued prematurely and the EOT visit was performed at the timing of a regular study visit and data were recorded on the eCRF in the EOT folder (i.e. EOT / Visit 8) but not in the regular study visits folder, then assessments will be mapped as follows:

- If EOT visit performed at the timing of Visit 3 / Month 6 (i.e. EOT visit date = study day 183 ± 14 days), then mapping to regular study treatment Visit 3
- If EOT visit performed at the timing of Visit 4 / Month 12 (i.e. EOT visit date = study day 365 ± 14 days), then mapping to regular study treatment Visit 4
- If EOT visit performed at the timing of Visit 5 / Month 18 (i.e. EOT visit date = study day 548 ± 14 days), then mapping to regular study treatment Visit 5
- If EOT visit performed at the timing of Visit 6 / Month 24 (i.e. EOT visit date = study day 730 ± 14 days), then mapping to regular study treatment Visit 6
- If EOT visit performed at the timing of Visit 7 / Month 30 (i.e. EOT visit date = study day 913 ± 14 days), then mapping to regular study treatment Visit 7
- If EOT visit performed at the timing of Visit 8 / Month 36 (i.e. EOT visit date = study day 1095 ± 14 days), then mapping to regular study treatment Visit 8

If study treatment was discontinued prematurely and the EOT visit was performed *not* at the timing of a regular study visit and data were recorded on the eCRF in the EOT folder (i.e. EOT / Visit 8), then assessments will be mapped to Visit “End of Treatment”.

For subjects who completed study treatment, data will be recorded on the eCRF in the EOT folder (i.e. EOT / Visit 8) and mapped to regular study treatment Visit 8.

Presentation of assessments/results in by-visit summary tables

In subject data listings, assessments/results from both scheduled and unscheduled visits will be presented. In summary tables, only assessments/results from scheduled visits will be presented.

Safety laboratory parameters

If the measured value is below the lower limit of quantification (LLOQ), half the value of LLOQ will be used in summary tables. A difference between two values below LLOQ will be assigned a value of zero.

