8.2 Post-study therapy

The study subject should be informed that there will be a loss of contraceptive protection after the end of the study treatment, i.e. after removal of the Mirena.

The investigator will counsel the subject about the contraceptive options available after the study treatment (at Visit 7, or before end of the study).

If pregnancy is not desired and if a woman wishes to continue using Mirena, a new system can be inserted immediately after removal any time during the cycle.

If a subject with regular cycles wants to start a different birth control method, time removal and initiation of new method to ensure continuous contraception. Either remove Mirena during the first 7 days of the menstrual cycle and start the new method immediately thereafter or consider starting the new method at least 7 days prior to removing Mirena if removal is to occur at other times during the cycle. If removal occurs at other times during the cycle and the woman has had intercourse in the week prior to removal, she is at risk of pregnancy.

If a subject with irregular cycles or amenorrhea wants to start a different birth control method, consider starting the new method at least 7 days before removal.

Post-study birth control counseling will be done according to standard of practice, without the sponsor's involvement.

9. Procedures and variables

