6.3 Pharmacokinetics/pharmacodynamics

6.3.1 Pharmacokinetics

Analyses will be performed based on the FAS.

The following will be determined at several timepoints according to Integrated Protocol Table 9-1:

- LNG concentrations in plasma
- Sex hormone binding globulin (SHBG) concentrations in serum

Data will be analyzed descriptively (including number of measurements, geometric mean with geometric standard deviation and coefficient of variation, arithmetic mean with arithmetic standard deviation and coefficient of variation, minimum, maximum and median) by time point (i.e. Visit 2 to Visit 8). Means at any time point will be calculated only if at least two-thirds of the individual data were measured and were above the LLOQ. For the calculation of the mean value a data point below LLOQ will be imputed by one-half of this limit. In tables showing mean values, where values below LLOQ are included in the calculation of mean values, these means will be marked.

The individual PK concentrations will be presented in the subject data listing.

Geometric mean concentration (\pm geometric standard deviation) curves of LNG and SHBG will be plotted versus time point using a linear and semi-logarithmic scale.

PK concentrations determined after Mirena expulsion/removal will not be included in the descriptive analyses and plots, but only be listed.

Furthermore, the residual content of LNG in used Mirena devices will be determined from all subjects at the end of treatment (i.e. from those who complete the 3 years in the study and from those who discontinue the study treatment prematurely). Data will be listed per subject and time point and individual data will be plotted versus time post baseline using a linear scale.

Residual contents with a partially missing or completely missing date of Mirena expulsion/removal will not be included in the plot, but only be listed.

Population PK analysis will be performed after Year 6, after Year 7 and at the end of study by the Modeling & Simulation (M&S) expert. A separate M&S Analysis Plan will be provided prior to the beginning of the population PK analysis by the M&S expert, including details of the planned model development and analysis. The results will be reported in a separate M&S Report by the M&S expert. A summary of the results will be provided in the Clinical Study Report.

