6.4 Safety

All safety variables will be analyzed based on the SAF, unless otherwise stated.

The main safety variable is the incidence of treatment-emergent AEs (both serious and non-serious). Treatment-emergent AEs are defined as any AEs occurring during the 'extension treatment period' starting at Day 1 of Year 6 of Mirena use. Further data rules are described in Section 4.7.

All AEs will be classified using MedDRA. The latest available version at the time of coding will be used. The results will be summarized on the level of SOC and PT, unless stated otherwise.

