6.4.3 Uterine bleeding / bleeding pattern

Recording and evaluation of bleeding data:

The occurrence of uterine bleeding will be recorded every day during the study treatment phase using eDiaries provided by the sponsor. The recording will start at the baseline visit and will be continued daily until Mirena is removed. Subjects are asked to rate their uterine bleeding in the past 24 hours on a daily basis according to the bleeding intensity definitions presented in Integrated Protocol Section 9.6.3.12 and Integrated Protocol Table 9–3.

Uterine bleeding data during the ‘extension treatment period’ starting at Day 1 of Year 6 of Mirena use will be analyzed according to the sponsor’s BPD “Recording and evaluation of bleeding data” (RD-SOP-1107) (1). Bleeding diary data prior to the ‘extension treatment

period' will not be included in the analyses described in this section. That means, for subjects who had her baseline visit prior to Day 1 Year 6, bleeding diary data between the baseline visit and Day 1 Year 6 will be excluded; for subjects who had their baseline visit after Day 1 Year 6, bleeding diary data between Day 1 Year 6 and baseline visit will not be recorded and will be considered as missing data entries. Bleeding diary data after Mirena expulsion/removal will not be included in the statistical analysis. Bleeding diary data after the date of premature discontinuation of study treatment period will not be included in the statistical analysis.

Besides the registration of absolute number of bleeding days, bleeding/spotting episodes will also be assessed according to the sponsor's bleeding intensity codes and the WHO definitions as provided in Integrated Protocol Section 10.3.2.3.2 and Integrated Protocol Table 10–2. This is possible because of the direct eDiary entry.

In addition to the WHO definitions, a “bleeding episode” is defined as day(s) with bleeding / spotting of which at least one day is of intensity 3 or higher, preceded and followed by at least 2 bleed-free days. There are examples given in the sponsor's BPD Section 1.4.1 which illustrate the advantage of this procedure. Another example is given in Integrated Protocol Section 10.3.2.3.2.

The bleeding patterns will be described using the reference period method recommended by the WHO, as given in the sponsor's BPD Section 1.4.3.

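### Treatment-emergent adverse events have no end at Mirena removal, so events from the roughly three weeks after removal count as extended use, mainly in Year 8

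*SAP*

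**What the plan says.** SAP 4.7 flags events by onset date with a lower bound only: "If an event occurred on Day 1 of Year 6 of Mirena use or later, it will be considered as treatment-emergent AE". The year of occurrence also follows the onset date. From Day 1 Year 6 + 365 to + 729 days, "it will be considered an AE in 7th year". From + 730 days there is no upper limit: "it will be considered an AE in 8th year (including any AE which may fall into the beginning of Year 9".

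The same section defines an end of treatment. For a woman whose device is expelled or removed, "the stop date of study drug administration will be the date of Mirena expulsion or removal". The adverse event rule does not use this date.

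SAP 6.4 ties the flag to a period: "Treatment-emergent AEs are defined as any AEs occurring during the" extension treatment period, which SAP 3 fixes at three years from Day 1 of Year 6.

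Four other provisions bear on the point:

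- Protocol 9.6.1.3 has adverse events recorded from consent to the end of study. Protocol 9.2 makes the end-of-study contact a call three weeks after the end-of-treatment (EOT) visit, at most three days early. Protocol Table 9–1 schedules adverse event collection only through Visit 8.
- Protocol 8.2 foresees replacement at the removal visit: "a new system can be inserted immediately after removal any time during the cycle".
- Two other data types are cut at removal. SAP 6.4.3: "Bleeding diary data after Mirena expulsion/removal will not be included in the statistical analysis". SAP 6.3.1: "PK concentrations determined after Mirena expulsion/removal will not be included in the descriptive analyses and plots".
- SAP 6.4.2 takes the denominator for each year's percentage as the women still on treatment when that year begins.

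**The concern.** Followed literally, SAP 4.7 books an event that starts after the study device is out as an event of extended use. That covers effects of a replacement Mirena or of another method. The benefit-risk section of the protocol (section 3) says that the infection risk from inserting an intrauterine contraceptive is limited to the first weeks after insertion, which is the same window. It also gives fewer insertions as a benefit of longer use. Complications of a new insertion should not be charged to the old device.

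The misattribution is uneven across years. In Years 6 and 7 only women who drop out have a removal; in Year 8 practically everyone still in the study does. Treatment-emergent adverse events are the main safety variable and are tabulated by year of use, so a reader of the final report could take a rise in Year 8 as an effect of duration.

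The numerator and denominator can also disagree. A woman removed late in Year 6 whose event starts early in Year 7 enters the Year 7 numerator but not its denominator.

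**Working it through.** **Inputs.** Protocol 10.4: 350 women, 15% dropout, 832 expected woman-years. Protocol 9.2: 18 to 21 days from EOT to the call; baseline 14 to 0 days before the end of Year 5; EOT up to 14 days early and not late. SAP 4.7: Month 36 is study day 1095. *Assumption:* the 15% is per year, which the protocol does not say.

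**Reproducing the plan's figure.** Women starting each year: 350, 350 × 0.85 = 297.5, 297.5 × 0.85 = 252.9; completers 252.9 × 0.85 = 214.9. Mid-year exposure: 323.8 + 275.2 + 233.9 = 832.8 woman-years, against 832 stated (a constant-hazard version gives 831.0). This supports the yearly reading.

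**Removals by year.** Dropouts in Years 6 and 7, then everyone still in the study in Year 8:

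| | Year 6 | Year 7 | Year 8 |
|---|---|---|---|
| Removals | 52.5 | 44.6 | 252.9 |
| Share of women starting the year | 15% | 15% | 100% |
| Share of all 350 removals | 15% | 13% | 72% |

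**Post-removal time.** Removals × 21/365, with dropouts spread evenly over the year, so that a share 21/(2 × 365) = 2.9% of their tails falls in the next year:

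| | Year 6 | Year 7 | Year 8 |
|---|---|---|---|
| Tail, woman-years | 2.9 | 2.6 | 14.6 |
| Relative to on-device exposure | 0.9% | 0.9% | 6.2% |

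With 18 days the last row is 0.8%, 0.8% and 5.4%.

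**Effect on event counts.** The documents give no event rates, so the ratio of the post-removal rate to the on-device rate is assumed. With 21 days, an equal rate inflates the counts by 0.9% / 0.9% / 6.3%, a doubled rate by 1.8% / 1.9% / 12.5%, and a fivefold rate by 4.5% / 4.7% / 31.3%.

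**Effect on the percentage of women with any event.** Let p be the yearly on-device incidence, q the chance of a new event after removal, and f the share with a removal. The percentage is p + (1 − p) × q × f, so the artificial Year 8 minus Year 6 gap is 0.85 × (1 − p) × q.

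- Assumed range p = 20% to 60%, q = 2% to 10%: from 0.85 × 0.4 × 0.02 = 0.7 points to 0.85 × 0.8 × 0.10 = 6.8 points.
- The upper end needs a post-removal rate of about eight times background: with p = 20% the 21-day hazard is −ln(0.8) × 21/365 = 0.0128, against −ln(0.9) = 0.105.
- At equal rates p = 1 − (1 − q)^(365/21). For q = 2%, 5% and 10% this gives p = 30%, 59% and 84%, and gaps of 1.2, 1.7 and 1.4 points.

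**Visit windows.** Removal on schedule falls at Day 1 Year 6 + 1066 to + 1094 days, and the tail ends at + 1087 to + 1115. Two things follow. An on-schedule event beyond + 1094, in Year 9, is a post-removal event. And a completer has 1066 − 730 + 1 = 337 to 365 on-device days in Year 8, or 358 to 386 with the tail, against 365 for a woman who continues through Year 6 or 7.

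**Denominator mismatch.** Women removed in the last 21 days of a year: 52.5 × 21/365 = 3.0 in Year 6 and 44.6 × 21/365 = 2.6 in Year 7.

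**The case against.** A reader might infer that the window is unlimited, that all post-removal events land in Year 8, and that Year 8 is bound to look worse. The documents do not support this. Recording ends at about three weeks. No adverse event assessment is scheduled after Visit 8, and Protocol 9.2.10 describes the call as one about pregnancy, so few events may be captured. Years follow the onset date, and about 28% of removals fall in Years 6 and 7. The tables are descriptive, with no planned test between years. Early visits can shorten on-device Year 8 time by up to four weeks, which partly offsets the tail.

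A reader might also treat removal events as contamination. Removal is a study procedure that the protocol sets out to evaluate, and under Protocol 9.7.3 removal pain is normally not recorded as an adverse event. Moving everything from the day of removal onwards out of the by-year tables would be unsound: expulsions, perforations and findings at the EOT examination can carry that date.

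Nor does SAP 6.4.2.1 intend to count perforations by a replacement device. It speaks of the Mirena, which SAP 6.1.3 describes as the one inserted five years earlier, and it censors women without an event at the stop date. What remains is that its MedDRA-term search has no device check.

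Finally, the open Year 8 bin was deliberate: the document history in SAP 7 records it under v5.0, before the final lock. It has a legitimate use, because a late EOT visit can put on-device events into Year 9. The SAP 4.3 rule that events count as treatment-emergent unless this can be ruled out concerns incomplete onset dates and does not settle the end of the window.

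These points limit the size. They do not supply an end relative to removal or resolve the conflict between SAP 3 and 6.4 and SAP 4.7.

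**Conclusion.** The point holds in a limited form. The flag has no end at the stop date, the open Year 8 rule conflicts with the three-year period, and device-free events are counted as extended use, unevenly by year. The exposure involved is about 0.9%, 0.9% and 6% of on-device time, given a yearly 15% dropout and a 21-day window.

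Year 8 *may* look somewhat worse. If the event rate after removal equals the rate before it, the gap in women with any event is at most about 1.7 points in the cases worked, before the offset from early visits. Gaps near 7 points need a much higher rate after removal and full capture. The denominator mismatch concerns about three women a year. Neither the Pearl Index nor any formal test is affected. This is a cheap improvement to the safety tables.

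**What to change.** 1. Reconcile SAP 3, 4.7 and 6.4 on when the treatment-emergent window ends.
2. In the by-year tables, count onset from Day 1 Year 6 up to and including the stop date of study drug administration. This keeps expulsions, perforations and EOT findings dated to that day. Keep on-device events that fall in Year 9 because of a late EOT visit.
3. Show events with onset after the stop date in a separate *after removal* column and leave the overall total unchanged. This also removes the denominator mismatch.
4. Identify removal-day procedure events with the field for causal relationship to protocol-required procedures, already collected under Protocol 9.6.1.2.3.
5. Add a study-device check to the MedDRA-term search for perforations in SAP 6.4.2.1.

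The cost is SAP wording, one extra column and two counts to explain. No new data are needed and no event is lost. Completers will have up to four weeks less observation in Year 8, which should be footnoted. The cut cannot separate effects of a method started before removal. On that, Protocol 7.4.1 and 8.2, which mention starting a new method about a week ahead, should be reconciled with Protocol 9.7.5, which restricts back-up contraception during treatment to barrier methods, and with exclusion criterion 14.
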